# Recommended for all patients:

PO Acetaminophen 1000 mg Q8H scheduled

- IV Naloxone 40-80 mcg PRN for respiratory depression (RR<10) or significant somnolence
- PO Benadryl 25mg Q4H PRN moderate to severe pruritis
- Recommended algorithm for transition to oral:
- PO Oxycodone 5mg Q4H PRN for pain 4-6
- PO Oxycodone 10mg Q4H PRN for pain 7-10
- Rescue PO Oxycodone 5mg Q2H PRN for pain 4-10 = only to be given as a 'rescue dose' if patient has persistent pain despite using Q4H PO oxycodone (breakthrough pain)
- Dosing and frequencies of medications in the above algorithms are recommendations. The recommended doses are not required for maintenance in the study and we anticipate that they may change given patient characteristics and variable response to medication, the rapidly evolving nature of acute pancreatitis, and hospitalist preferences. However, the mode of IV opioid administration (PDA vs PCA) should remain as assigned until transition to PO opioid.
- Each patient will be closely monitored for adverse events related to opioid
  administration to include cardiorespiratory decompensation, hemodynamic
  instability, nausea, vomiting, confusion, altered mental status, headache,
  drowsiness, etc. This monitoring will include continuous pulse oximetry in addition to
  vital sign measurement every 4 hours.
- The efficacy of each treatment arm to adequately control the patient's pain will be assessed with scheduled use of the Numeric Rating Scale (NRS) every 4 hours by the nursing staff. Pain rating on the NRS will be documented by the nursing staff after each assessment. In an NRS, patients are asked to circle the number between 0 and 10 that fits best to their pain intensity. Zero usually represents 'no pain at all' whereas 10 represents 'the worst pain ever possible'.
- Likert scale of 1 to 10 (1 = Very poor, 10= excellent) will be used to grade overall patient satisfaction with pain control.
- Once each patient's pain is well controlled on IV opioid administration (as determined by the attending physician) and they can tolerate intake by mouth, transition from IV to PO opioid medication can be made in each arm by the attending physician. If the patient is unable to tolerate either the PDA or the PCA arm for any reason and requires switching over to the other arm as part of his/her clinical care, they will be withdrawn from the study and their data will be excluded while analyzing the results. AP has a variable course and may require IV opioids

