after transition to PO opioids. The modality of IV opioid administration will revert to the assigned treatment arm.

- Other aspects of each patient's routine clinical care will continue as per the attending physician under whom the patient is admitted regardless of treatment arm status (PDA vs PCA).
- At the end of their hospital stay, we will document the following outcomes:
  - 1. Primary outcome: Length of stay (days)
  - 2. Secondary outcomes:
  - a. Number of hours the patient is NPO before diet is initiated
  - b. Mean pain scores on NRS over the first 24 hours, second 24 hours and course of their hospital stay
  - c. Total opioid dose for pain control during hospitalization (average MME during hospital stay)
  - d. Time to transition to PO opioids
  - e. Opioid-related adverse events/side effects: respiratory decompensation, sleep-disordered breathing, hypotension, nausea, vomiting, constipation, drowsiness, confusion, delirium or other mental status changes, myoclonus, headache, urinary retention, physician suspected opioid abuse or any form of allergic reaction.
  - f. Use of naloxone and antiemetics
  - g. Number of rescue doses required daily and in total through the hospital stay
  - h. ICU transfer
  - i. 30-day readmission rates
  - j. All-cause inpatient mortality and opioid-related inpatient mortality
  - k. 30-day mortality
  - I. Daily MME on discharge
- We expect to enroll patients over a 36-month period from the start date of the study. Based on this, we expect patient enrollment to end by 4/30/2024. We will plan to perform data analysis at two points: 1. Interim data analysis at a predetermined point in the study (mid-point of study), and 2. At the end of the study once patient enrollment has been completed.

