#### B. Statistical Considerations

# a. Sample Size Justification:

- Data from a retrospective study of acute pancreatitis patients receiving either patient-controlled analgesia (PCA, n=116) or conventional IV push (IVP, n=647) showed that mean length of stay was higher in the PCA group (9.9 ± 7.14 days) compared to the IVP group (6.4 ± 9.86 days). The effect size calculated using this data yielded a Cohen's d=0.42. Therefore, assuming a 5% error probability for two groups, the estimated sample size to achieve 80% statistical power was determined to be 87 patients per group. At the midpoint of the study when half of target sample size is reached, preliminary post-hoc analysis will be performed to determine effect size and statistical power.

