#### **B4. POSSIBLE BENEFITS**

Patients in this study will obtain no direct benefits from participation in the study. We hypothesize that based on prior studies in postsurgical patients, patients in the PCA arm may potentially have better control of their AP-related pain as compared to conventional physician directed analgesia. This may potentially result in higher patient satisfaction, early transition to oral analgesics, and shorter hospital stays. This information will be helpful in better management of the patients' pain with a PCA protocol in the future.

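### The mean pain score for the second 24 hours exists only for patients still in hospital, and the plan has no rule for those discharged earlier

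*Combined protocol and SAP*

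**What the plan says.** B3.A lists as secondary outcome (b) the mean NRS pain score over three periods: the first 24 hours, then the "second 24 hours and course of their hospital stay". The scores come from "scheduled use of the Numeric Rating Scale (NRS) every 4 hours by the nursing staff", so a full 24-hour window holds about six. The outcome list opens with "At the end of their hospital stay, we will document the following outcomes", and no NRS after discharge is described.

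B3.B.b compares primary and secondary outcomes by independent-samples t-test or Mann-Whitney U. It gives no rule for missing scores, for a window cut short by discharge, or for a patient who left before the window opened. Nothing says whether hour 0 is ED arrival, admission, randomisation or first dose.

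Length of stay is the primary outcome. On how it may differ by arm, the document points two ways. B3.B.a cites a retrospective study in which "mean length of stay was higher in the PCA group (9.9 ± 7.14 days") "compared to the IVP group (6.4 ± 9.86 days"). B4 expects that better pain control with PCA may lead to "early transition to oral analgesics, and shorter hospital stays".

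**The concern.** A fixed 24-48 h window removes the problem of unequal averaging periods. It does not settle who has a value. A patient who leaves before the window opens has no mean. One who leaves during it has a mean built from a few early scores.

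By the plan's own reasoning, leaving is related both to treatment (it is the primary outcome) and to pain (B4). Comparing the available means therefore compares groups that have been selected after randomisation. If comfortable patients leave first, the arm that discharges sooner keeps its more painful patients in this outcome, and can look worse on pain when true pain is the same. Pain control is the direct benefit hypothesised in B4, so a distorted pain comparison matters even as a secondary outcome. The primary analysis is unaffected.

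**Working it through.** **Step 1. The plan's own figure.** With d = 0.42, two-sided 5% and 80% power, n = 2(1.96 + 0.84)²/0.42² ≈ 89 per group by normal approximation, close to the stated 87. I use 87 per arm below.

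**Step 2. Who would lack scores.** B3.B.a gives only means and SDs, so a shape must be assumed. For a log-normal, σ² = ln(1 + (SD/mean)²) and μ = ln(mean) − σ²/2.
- IV push (6.4, SD 9.86): σ² = 1.216, σ = 1.103, μ = 1.248. P(stay < 1 day) = Φ(−1.248/1.103) = Φ(−1.13) = 12.9%. P(stay < 2 days) = Φ((0.693 − 1.248)/1.103) = Φ(−0.50) = 30.7%.
- PCA (9.9, SD 7.14): σ² = 0.419, σ = 0.647, μ = 2.083. P(stay < 1 day) = Φ(−3.22) = 0.06%. P(stay < 2 days) = Φ(−2.15) = 1.6%.

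With the clock at admission, the 1-day figures are the patients with no score in the window (about 11 v 0 of 87). The 2-day figures are those without a full window.

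| Stay shape (assumed) | No score in window, IV push v PCA | No full window, IV push v PCA |
|---|---|---|
| Log-normal | 13% v 0.1% | 31% v 2% |
| Gamma | 35% v 2% | 46% v 7% |
| Weibull | 29% v 3% | 43% v 9% |
| Normal | 29% v 11% | 33% v 13% |

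If the clock starts one day after admission, the log-normal share leaving before the window opens is P(stay < 2 | stay > 1) = (30.7 − 12.9)/(100 − 12.9) = 20% for IV push and 1.5% for PCA.

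**Step 3. What that does to the comparison.** Assumptions, none of them in the documents: NRS SD 2, identical true pain in both arms, and correlation ρ between stay and pain (normal scale), with the shortest stays leaving. If a fraction f has no score, the mean of those remaining rises by ρ × 2 × φ(z)/(1 − f), where Φ(z) = f. The false difference D is the gap between the two arms' shifts. Its standard error is 2√(1/[87(1 − f₁)] + 1/[87(1 − f₂)]). The false-positive rate is P(Z > 1.96 − D/SE) + P(Z < −1.96 − D/SE).

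For 12.9% v 0.06%, φ(z)/(1 − f) is 0.241 and 0.002, so D = 2ρ × 0.239. The SE is 2√(1/75.8 + 1/86.9) = 0.314.

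| No score in window | D at ρ = 0.3 / 0.5 / 0.7 | False-positive rate |
|---|---|---|
| 12.9% v 0.06% (log-normal, clock at admission) | 0.14 / 0.24 / 0.33 | 7% / 12% / 19% |
| 20.5% v 1.5% (log-normal, clock one day later) | 0.19 / 0.32 / 0.45 | 9% / 17% / 28% |
| 35% v 2% (gamma, clock at admission) | 0.31 / 0.52 / 0.73 | 15% / 33% / 57% |
| 15% v 5% (illustrative) | 0.10 / 0.17 / 0.23 | 6% / 8% / 11% |
| Equal loss in both arms | 0 | 5% |

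These rates cover only patients with no score. Patients who leave mid-window keep a mean, but one drawn from the early hours only. That effect is not modelled here and need not act in the same direction.

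**The case against.** **Early discharge may be rare.** B2 says adequate control often needs IV opioids for the first 24-48 hours. B3.C excludes patients discharged from the ED, and B3.A makes the oral switch depend on controlled pain and tolerance of intake. An SD larger than the mean mostly reflects a long right tail, so a two-moment fit says little about the left one. This stands: it weakens the high-loss rows, the gamma row above all. It does not show that losses are nil or equal by arm.

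**The stay figures are weak evidence for this trial.** They come from a non-randomised comparison (116 v 647), so the gap need not be an effect of how analgesia is given. B4 expects the opposite direction. This also stands, and it means the sign of the bias cannot be stated.

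**Two stronger readings are tempting.** A reader might infer that discharge removes 31% of one arm and 2% of the other. Those are patients without a complete window, and one who leaves at 30 or 40 hours still has scores and a mean. A reader might also infer that the bias would reverse the pain result. The calculation only adds a shift when true pain is identical. The documents give no true pain difference for that shift to overturn.

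**It is one of three pain summaries within one of twelve secondary outcomes.** True, and it limits the weight of the point. The correction is cheap all the same.

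**Conclusion.** The structural point holds without any distributional assumption: the second-24-hour mean depends on still being an inpatient, discharge is the primary outcome and is expected to follow pain control, and the plan has no rule for it.

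The size is much less certain. With a log-normal stay and the clock at admission, about 13% v 0.1% would have no score. With NRS SD 2 and correlation 0.3-0.7, that gives a false difference of 0.14-0.33 points and a false-positive rate of 7-19% against a nominal 5%. The shape, SD and correlation are all assumed, and other shapes give larger losses. If few patients leave early, or stays are similar by arm, the bias is small. Which arm would be penalised is unknown.

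The plan should be changed on this point. It is not a threat to the primary result.

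**What to change.** 1. Define hour 0 as randomisation. B3.C allows floor admission up to 48 hours after ED arrival in its table (its text says within 24 hours), and recruitment begins on the floor. A clock started at arrival could therefore place much of the scored time before allocation.
2. Replace the available-case 24-48 h test with a mixed model on all 4-hourly NRS values from randomisation to 48 h, with arm, time and their interaction, and report the arm contrast averaged over 24-48 h. Include every randomised patient. B3.A currently drops those who switch arm, so the text must say that this analysis keeps them.
3. Report per arm how many patients contribute any score, and how many a full set, in each window.
4. Add a sensitivity rank comparison in which patients discharged alive before the window take the best rank, deaths the worst, and all others are ordered by their available mean.

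Cost: revised wording and modest extra analysis on scores already charted. The mixed model assumes that discharge depends on scores already observed. The rank analysis does not need that assumption, but it counts early discharge as a good outcome, so it partly measures stay as well as pain. The two should be read together.

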## **B2. SIGNIFICANCE AND BACKGROUND FOR THE STUDY**

AP represents a critical health concern nationwide, with estimated 274,000 admissions annually and at a cost of 2.6 billion dollars. Current treatment strategies for AP are limited to supportive care with fluid resuscitation, analgesia, nutrition and prevention of end organ damage. Abdominal pain is often the predominant symptom in patients with AP and is treated with analgesics. As there is currently no disease-specific medical treatment to change the natural history of pancreatitis, pain control remains central to the treatment of AP (1). Among the analgesics, opioids have been shown to be provide safe and effective pain control in patients with AP. Current literature shows that there is no difference in the risk of pancreatitis complications or clinically serious adverse events between opioids and other analgesia options (2). Among hospitalized AP patients, adequate pain control often requires the use of intravenous (IV) opiates in the first 24-48 hours, which can later be transitioned to oral (PO) opioids. While there are various methods of delivering opioid medications such as IV. PO. and transdermal to name a few, IV opioids are commonly administered, either on a scheduled and/or on an as needed (PRN) basis as directed by the attending physician. In contrast to the conventional, method of physician directed IV opioid delivery, PCA is a form of IV opioid medication delivery in which the patient can rapidly titrate the opioid dose to manage variable levels of pain (3). This modality of opioid administration is often preferred by patients and has been widely used in postsurgical and obstetric patients to effectively treat their pain (4-6). PCA allows for faster intervention on pain limiting time to treatment and peak pain levels and has also been shown to decrease total opioid dose. However, there is limited evidence in published literature assessing the feasibility of using PCA to treat the pain of AP or comparing its efficacy and safety profile compared to the more traditional physician directed analgesia. One retrospective study has shown that use of PCA was surprisingly associated with longer hospital stays and higher rates of outpatient opioid use when compared to PDA, however there are no prospective trials to study this comparison (7). Hence, in this study, we compare the effects of using PCA among patients with AP to that of conventional PDA.

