#### **B3. DESCRIPTION OF RESEARCH PROTOCOL**

A. Study Design – Overview, Methods, Procedures

- We will identify patients with AP based on the 2012 revised Atlanta criteria for diagnosis,
   i.e., AP is diagnosed if 2 out of the following 3 criteria are met:
- Acute onset of persistent, severe, epigastric pain often radiating to the back,
- Elevation in serum lipase or amylase to three times or greater than the upper limit of normal,
- Characteristic findings of acute pancreatitis on imaging (contrast-enhanced computed tomography [CT], magnetic resonance imaging [MRI], or transabdominal ultrasonography).
- Patients will be recruited for participation in this study while they are hospitalized with AP at Beth Israel Deaconess Medical Center. Once the patient has been transferred from the ED to the hospital floor, we will identify and recruit them for participation in our study.
- After obtaining informed consent from the patient, the patient will be enrolled by simple randomization to either the PCA or the PDA arm of the study. The research staff will assign patients to either the PCA arm or the PDA arm based on a standard randomization. Once, a patient has consented, the research staff will assign them to the next sequential study ID and corresponding study arm and let the attending hospitalist know of the result. The patient will then be enrolled in their assigned arm.
- The initial protocol for analgesic administration in each arm is as follows:

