# C. Subject Selection

We will study 174 patients admitted within 24 hours to the hospital with AP between 18 and 65 years of age. Patients will be randomized to receive IV opioids either via PCA (n=87) or PDA (n=87). Exclusion criteria are as follows: known allergy or contraindication to opioids, active illicit drug use, chronic pancreatitis, pancreatic cancer, acute encephalopathy/psychiatric illness that would preclude ability to use PCA, chronic renal insufficiency with a Cr >2, acute renal insufficiency with a Cr >3, and known allergy to acetaminophen or hepatic dysfunction otherwise limiting acteaminophen use.

Inclusion criteria	Exclusion criteria
Diagnosis of AP confirmed by revised Atlanta criteria	Active illicit drug use
	Discharged from the ED
Admitted to the medical floor within 48 hours of ED arrival	Direct admission to ICU from ED
	Known allergy to opioid medications
Age 18-65	Age <18 or >65
	Known chronic pain syndrome or concurrent medical condition with chronic pain
	Active
	encephalopathy/confusion/delirium/psychiatric

Study Description – Part B CCI Form: 9-2015 PI Revision Date: 3/2/2021

illness or any other condition that limits capacity
Known chronic opioid use
Renal insufficiency (baseline Creatinine of >2 and/or AKI with Cr>3 on admission)
Known allergy to acetaminophen or hepatic dysfunction otherwise limiting acetaminophen use

Subjects will be enrolled without regard to race, gender, or vulnerable category status.

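### Minor: secondary outcome (c) does not say whether opioid use is a patient total or a daily average, and the windows for (b) and (c) are not tied to randomisation

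*Combined protocol and SAP*

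**What the plan says.** Section B3.A gives secondary outcome (c) as "Total opioid dose for pain control during hospitalization (average MME during hospital stay". Nothing says what the average is taken over. Other items in the list do state their time unit: (g) is "Number of rescue doses required daily and in total through the hospital stay", and the last item is "Daily MME on discharge". Section B3.B.b (Data Analysis) refers back to the list and names the tests. It adds no definition of MME, of averaging or of a window.

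The background in B2 speaks of a total: PCA "has also been shown to decrease total opioid dose".

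Item (b) is "Mean pain scores on NRS over the first 24 hours, second 24 hours and course of their hospital stay", with no starting point for the first 24 hours. On timing, B3.A says: "Once the patient has been transferred from the ED to the hospital floor, we will identify and recruit them". Consent and randomisation come after that. The inclusion table in B3.C allows "Admitted to the medical floor within 48 hours of ED arrival", although the opening text of that section refers to 24 hours. Under B6, research staff look for new patients daily.

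On length of stay, B3.B.a cites a retrospective study that "showed that mean length of stay was higher in the PCA group" (9.9 against 6.4 days). B4 hypothesises that PCA may shorten stay.

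**The concern.** A total and a daily average are different outcomes. The daily average divides by length of stay, which is the primary outcome and is measured after randomisation. If stay differs between arms, one measure could show less opioid use with PCA and the other more. The text leaves the choice open until data are seen, including at the planned mid-study analysis.

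The second issue is the clock. Time before assignment cannot be affected by the assigned mode of analgesia. Pain scores and opioid doses from that time, if counted, add the same kind of exposure to both arms and dilute any difference between them.

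**Working it through.** The plan gives no figure for outcome (c), so there is none to reproduce.

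**1. When do total and daily MME disagree?**

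Inputs: mean stays of 9.9 days (PCA) and 6.4 days (IV push) from B3.B.a. A PCA stay of 5.0 days is an assumption, chosen only to represent the shorter stay hypothesised in B4.

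Let r be the PCA/PDA ratio of daily MME. Then

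ratio of totals = r × ratio of mean stays.

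This is exact if daily MME is the arm's MME divided by the arm's inpatient-days. For arm means of patients' own daily averages, it requires daily dose to be independent of stay.

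- *PCA stays longer (planning means).* Stay ratio = 9.9/6.4 = 1.547. The total is higher with PCA while the daily dose is lower when 6.4/9.9 < r < 1, that is 0.646 < r < 1. Example with an assumed PDA level of 30 MME/day and r = 0.8: PCA 24 × 9.9 = 237.6, PDA 30 × 6.4 = 192.0. PCA is 20% lower per day and 24% higher in total. The limit 0.646 does not depend on the 30 MME/day.
- *PCA stays shorter (assumed 5.0 days).* Stay ratio = 5.0/6.4 = 0.781. The total is lower with PCA while the daily dose is higher when 1 < r < 6.4/5.0, that is 1 < r < 1.28. Example: r = 1.10 gives a total ratio of 1.10 × 5.0/6.4 = 0.86.
- *Arm mean of patients' totals.* There is only one measure, so no disagreement can arise.

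These ranges concern the direction of the point estimate, not statistical significance.

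**2. How much of a 24-hour window could precede assignment?**

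Suppose windows are counted from ED arrival and assignment occurs h hours later. With evenly spaced scores and a constant effect after assignment, the expected difference in the first-24-hour mean is multiplied by (24 − h)/24 for h up to 24. At h = 24 the factor is (24 − 24)/24 = 0, so the first window lies wholly before assignment. At h = 48, the limit in the inclusion table, the second window does too.

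**3. Do early windows from randomisation remove the dependence on stay?**

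They reduce it but do not remove it. As an illustration, fit lognormal stays (an assumed shape) to the quoted means and SDs (9.9 ± 7.14 and 6.4 ± 9.86 days). The log-SD is √ln(1 + (SD/mean)²), which gives 0.647 and 1.103. The median is mean/exp(log-SD²/2), which gives 8.03 and 3.48 days. The share of stays under 2 days is then:

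- PCA: Φ(ln(2/8.03)/0.647) = Φ(−2.15), about 2%
- IV push: Φ(ln(2/3.48)/1.103) = Φ(−0.50), about 31%

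Stay is counted here from admission. Under this model, dose in the 24-48 h window would still be cut short by discharge more often in one arm.

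**The case against.** The strongest reply is that the text already leans to the harmless reading. Item (c) is labelled a total, B2 argues from total dose, and the items that mean per day say so. B3.B.b presents data as mean ± SD, so an average MME fits the arm mean of patients' totals. This stands, and it is why the point is minor. It does not settle the matter: the bracket attaches the average to the hospital stay rather than to patients, and item (b) uses a mean over time within a patient.

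A second reply is that the total is no cleaner than the daily measure, because it accumulates over the same stay. This also stands. The defect is that the plan does not name its measure, not that one of the two is free of stay.

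A third is that the planning means come from non-randomised data and run against the trial's own hypothesis. That is fair, so both directions are shown above.

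A reader might infer that (c) is a per-day outcome and that its result will therefore be reversed. The documents do not support this. They never state a per-day denominator for (c), and they give no MME figures from which the chance of a reversal could be judged.

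**Conclusion.** The point holds as a minor one, confined to secondary outcomes. The wording of (c) admits two readings, of which the patient total is the more natural. If the daily reading were used, the two measures would disagree in direction for a daily-dose ratio of 0.646 to 1 under the planning means, or of 1 to 1.28 with an assumed 5.0-day PCA stay. Both ranges rest on the multiplicative relation above and on stay differing by arm. How likely either is cannot be said.

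The starting point of the windows in (b) and (c) is also unstated. A reader might infer that the plan does count from ED arrival. It does not say so; it only leaves this possible, and floor transfer may come as late as 48 hours after arrival. The amount of dilution is therefore unknown.

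**What to change.** Before any comparison by arm is seen:

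- Define (c) as each patient's cumulative MME, IV plus PO, from randomisation to discharge, compared between arms as patient totals. Report MME per day as a separate, named descriptive measure, as (g) already does for rescue doses.
- Start the 24-hour pain-score windows in (b) at randomisation.
- Add cumulative MME over 0-24 h and 24-48 h from randomisation, labelled supportive. State that the second window is still affected by early discharge, and report the number still in hospital in each arm.
- Where a pain score from before randomisation is already charted, adjust the (b) window means for it by ANCOVA to gain precision.

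The rewording costs nothing. The windowed MME needs dose times from the medication record; these are assumed to be available, since the documents do not list them as study data. There are two extra supportive comparisons. Patients discharged before 48 hours contribute dose only up to discharge, which needs a footnote.

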# b. Data Analysis:

- Primary and secondary outcomes of interest will be studied as outlined above. Data will be presented as mean ± standard deviation, median [interquartile range; range], and count (percentage), as appropriate. Data will be graphed, QQ plots performed and Shapiro-Wilk test utilized to assess for normality. Statistical tests for primary and secondary outcome will be compared using independent samples t-test and Mann-Whitney U test, as appropriate. Categorical variables were investigated using Pearson's Chi-Square. Statistical significance will be assigned at 0.05. All data will be analyzed using the R statistical software.

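### Opioid adverse events and naloxone/antiemetic use have no stated observation window, so a whole-stay comparison reflects both the delivery mode and the days observed

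*Combined protocol and SAP*

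**What the plan says.** The outcome list in B3.A opens with "At the end of their hospital stay, we will document the following outcomes". Under it:

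- Item (e) is a list of events, beginning "Opioid-related adverse events/side effects: respiratory decompensation, sleep-disordered breathing, hypotension, nausea, vomiting, constipation, drowsiness, confusion, delirium or other mental status changes, myoclonus, headache". It gives no period, rate or time-to-event definition.
- Item (f) reads, in full, "Use of naloxone and antiemetics". Again there is no period or denominator.
- Item (g) is "Number of rescue doses required daily and in total through the hospital stay": a daily count and a whole-stay total.
- Item (b), mean pain score, is the only item with early fixed windows: the first and second 24 hours, as well as the whole stay.
- Items (i) and (k), readmission and mortality, run to 30 days. No adverse-event collection after discharge is described.

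Length of stay is the primary outcome. B3.B.a plans on a retrospective mean of 9.9 days (SD 7.14) with PCA and 6.4 days (SD 9.86) with conventional IV push. B4 expects the opposite direction, hoping that PCA brings "higher patient satisfaction, early transition to oral analgesics, and shorter hospital stays". B3.B.b names the t-test and Mann-Whitney U test for outcomes and adds "Categorical variables were investigated using Pearson's Chi-Square". It mentions no patient-days, offset or time-to-event method.

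**The concern.** If (e) and (f) are tallied when the patient leaves, observation ends at discharge, and the time to discharge is the quantity the trial is designed to find different. The arm that stays longer is watched for more days and will tend to record more events at the same daily risk. In the arm that leaves sooner, later constipation or urinary retention, for example, goes unseen.

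The stake is how the safety results are read. B5 names a higher opioid dose in a short time as the specific risk of the PCA pump. If PCA shortens stay, a whole-stay comparison tends to understate any added daily risk from PCA; if PCA lengthens stay, it tends to overstate it. A reader given only whole-stay percentages cannot separate the mode from the days watched.

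**Working it through.** **Inputs from the documents.** Mean stays 9.9 and 6.4 days with SDs 7.14 and 9.86, d = 0.42, 5% error, 80% power and 87 per group (B3.B.a); Pearson chi-square (B3.B.b). **Assumed, because the documents give no figure:** a daily risk h of a first event of 2%, 5% or 10%, the same in both arms; two-sided testing; (e) and (f) analysed as any event during the stay.

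**Plan's own figure.** n = 2(1.96 + 0.8416)²/0.42² = 89 per group, close to the stated 87. Power at 87 is 79.1%. The sample size is not at issue here.

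**Days observed.** 9.9/6.4 = 1.55, so expected whole-stay counts are 55% higher in the longer-staying arm at identical constant daily risk.

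**Constant daily risk.** P(any event) = 1 − exp(−h × days). Rejection probability is Φ[(|a − b| − 1.96√(2p̄(1 − p̄)/87)) / √(a(1 − a)/87 + b(1 − b)/87)], where a and b are the two arms' event proportions and p̄ is their mean.

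| h per day | 6.4 days | 9.9 days | Rejection |
|---|---|---|---|
| 2% | 12.0% | 18.0% | 19-20% |
| 5% | 27.4% | 39.0% | 37% |
| 10% | 47.3% | 62.8% | 54% |

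For the 5% row: (0.1165 − 1.96 × 0.0714)/0.0709 = −0.33, and Φ(−0.33) = 0.37. Summing the two binomial distributions exactly gives 19%, 37% and 57%.

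**Risk falling to a quarter after day 2.** B2 says IV opioids are often needed in the first 24-48 hours, so this case is plausible. Effective days are 2 + 4.4/4 = 3.1 and 2 + 7.9/4 = 3.975.

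| Initial h per day | Shorter stay | Longer stay | Rejection |
|---|---|---|---|
| 2% | 6.0% | 7.6% | about 6% |
| 5% | 14.4% | 18.0% | about 10% |
| 10% | 26.7% | 32.8% | about 14% |

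**Other cases.**
- Equal stays: the event proportions are equal and rejection returns to the nominal 5%.
- Stays of 6.4 and 8.4 days at constant risk: about 10%, 17% and 24%.
- Stays that vary between patients, as gamma distributions with the planning means and SDs, at constant risk: about 24%, 59% and 89%. The table at mean stays is therefore not an upper limit.

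**Rescue doses (g).** Simulated with gamma stays of at least one day and 0.5 to 2 doses per day in both arms, the whole-stay total rejects about 64-68% of the time by t-test and about 99% by Mann-Whitney. The per-day count rejects 5.0-5.6% of the time.

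**Check on possible remedies.** Two limits follow from the same inputs.
- A simple rate per patient-day is neutral only if risk is roughly constant. In the falling-risk case the rate ratio, longer to shorter stay, is (3.975/9.9)/(3.1/6.4) = 0.40/0.48 = 0.83, because the extra days are low-risk days.
- A fixed window does not fully equalise observation if many patients leave within it. With gamma or lognormal stays matching the planning means and SDs, about 45-54% of IV-push stays but 6-13% of PCA stays end before 72 hours. Before 48 hours the figures are about 31-46% and 2-7%. These depend heavily on the assumed shape.

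**The case against.** Four points have force.

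1. **Rescue doses.** A reader might infer that (e), (f) and (g) are all measured only over the whole stay. The documents do not support that for (g), where a daily count is already planned. Only the total in (g) is affected.
2. **The window for (e) and (f) is inferred.** The lead-in sentence says when outcomes are documented, and neither item states ever/never coding. Whole-stay incidence with chi-square is the natural reading, but it is not written. This stands, although leaving the window open is itself a gap.
3. **Whole-stay incidence is a legitimate randomised comparison.** Length of stay follows from assignment, and more events because a strategy keeps patients in hospital longer is a real consequence of that strategy. A reader might conclude that the whole-stay result is invalid, or that the rejection rates above are false positives outright. They are false positives only if the result is read as a difference in daily risk, which the protocol does not claim to estimate.
4. **The larger figures need constant risk.** B2 and the oral-transition step in B3.A suggest that opioid risk is concentrated early, which brings rejection down to about 6-14%.

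In addition, 30-day readmission and mortality capture some serious harm after discharge in both arms. None of this supplies an analysis of (e) and (f) that allows for days observed.

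**Conclusion.** The point holds for (e), (f) and the total in (g). As written, the comparison would mix delivery mode with days observed, and the plan has no analysis that separates them. The size is uncertain: from about 6% rejection at equal daily risk (2% per day, falling after day 2) to 54% (constant 10% per day) at the planning mean stays, and no excess if stays do not differ. The daily risks and their time course are assumptions, and the planning stays come from retrospective data whose direction is opposite to the hypothesis in B4. The primary outcome is unaffected. The change is still worth making, because these items are the trial's main evidence on opioid safety and the plan already uses the remedy for pain scores and rescue doses.

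**What to change.** - **(e) and (f):** state the window and the coding. Add a comparison that accounts for time observed: time to first event censored at discharge, or events per patient-day from a count model with a log-days offset. Because a simple rate can over-correct when risk falls over the stay, prefer the time-to-event form or include hospital day in the count model. Discharge is not independent of recovery, so describe the result as in-hospital risk.
- **Early windows:** report (e) and (f) also for the first and second 24 hours, as in (b), giving the starting point of the clock (which (b) leaves open) and the number still in hospital at the end of each window. A 72-hour window should not be relied on alone, for the reason shown in the working.
- **(g):** name the daily count, shown by hospital day, as the main measure and the total as descriptive.
- **Whole-stay counts:** keep them, labelled as total burden and shown with patient-days observed in each arm.

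Cost: a change of wording and a little more analysis. The day of each event must be recorded; the documents do not say that adverse events are time-stamped, so the data form may need a field. Early windows miss later events, which would appear only in the time-based and whole-stay tables.
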